# 2.2 Secondary Objectives

- To describe the immunogenicity of Tri-NIV at 2 different doses, and the licensed comparator Fluzone HD (Sanofi Pasteur) based on hemagglutination inhibition (HAI) responses to at least 2 historic and/or drifted A virus strains (one H1N1 and one H3N2).
- To describe the immunogenicity of Tri-NIV at 2 different doses, and the licensed comparator Fluzone HD (Sanofi Pasteur), based on microneutralization (MN) responses to vaccine-homologous and historic and/or drifted influenza A strains, and the vaccine-homologous B/Victoria lineage strain, at Day 21 post-dosing.

# 2.3 Exploratory Objectives

- To describe the immunogenicity of Tri-NIV at 2 different doses, and the licensed comparator Fluzone HD (Sanofi Pasteur), based on HAI and MN responses to a contemporary B/Yamagata lineage strain Day 21 post-dosing.
- To describe the immune response to Tri-NIV at 2 different doses, and the licensed comparator Fluzone HD (Sanofi Pasteur), as measured by competitive-binding assays using purified HA and broadly-neutralizing HA monoclonal antibodies of varying specificities on Days 0 and 21.

# 3 TRIAL OVERVIEW

## 3.1 Design

This is a Phase 1/2, randomized, observer-blinded, active-controlled clinical trial. Approximately 330 eligible subjects will be enrolled and randomized into 1 of 3 treatment groups, as shown in Table 1. Each group will consist of approximately 110 subjects total, stratified by age (60 to < 75 and  $\geq$  75 years), gender, and history of receipt of 2016 - 17 influenza vaccine.

On Day 0, subjects in Groups A and B will be administered an IM injection of 15 or 60  $\mu$ g HA per strain of Tri-NIV in a 0.3 or 0.8 mL volume, respectively; subjects in Group C will receive the preconfigured comparator (Fluzone HD) at the manufacturer's recommended dose and volume. On Day 21, all Group A and B subjects will be administered a rescue injection with a licensed seasonal influenza vaccine, while all Group C subjects will be administered an injection with sterile saline placebo (in a total volume of 0.5 mL) to maintain trial blind. Trial follow-up for each subject will span approximately 1 year from the Day 0 injection. It is anticipated that a percentage of the randomized trial subjects will not complete the trial. Subjects who withdraw or are discontinued will not be replaced. The maximum duration of the trial will be approximately 1 year for each subject.

Enrollment will be divided into 2 stages. Stage 1 will enroll a group of approximately 60 subjects (approximately 20 subjects per treatment group) and Stage 2 will enroll the remainder of the subjects per treatment group. The only difference in the 2 stages will be a safety review in-clinic visit for Stage 1 subjects on Day 7 (+1 day) of the trial, whereat subjects will be asked to present their subject diaries. In Stage 2, a safety review telephone call on Day 7 (±1 day) of the trial will replace the clinic visit. Progression from Stage 1 to Stage 2 will require favorable review of cumulative Stage 1 safety against vaccination holding rules as defined in Section 3.1.1.1.

## 3.1.1 Safety Monitoring of Enrollment and Vaccinations

This will be a first-in-human trial with Tri-NIV formulated with Matrix-M1 adjuvant. Thus, vaccination holding rules will be used to govern progression from the Stage 1 group to full enrollment in Stage 2. Solicited and unsolicited AEs reported from all Stage 1 subjects within 7 days of Day 0 vaccination will be evaluated against vaccination holding rules (3.1.1.1). These AE data will be summarized by the sponsor statistician, reviewed, and provided to an independent medical monitor in aggregate form (without unblinding or subdivision by treatment group). If vaccination holding rules are not met, the independent medical monitor will notify the sponsor Chief Medical Officer (CMO) to proceed with enrollment of subjects. If vaccination holding rules are met, the independent medical monitor will notify the sponsor CMO who will pause enrollment pending further review and request unblinding of the data. The independent medical monitor and the sponsor will review the unblinded data and develop a report and recommendation to either: a) resume enrollment, b) amend the protocol and resume enrollment, or c) terminate the protocol. The report, the recommendation, and the amended protocol and

ICF (if relevant), will be provided to the IRB and CBER, and enrollment will not recommence until IRB approval is obtained.

## 3.1.1.1 Vaccination Holding Rules

Adverse event reports meeting any one of the following 2 criteria will result in a hold being placed on subsequent enrollment and vaccinations, pending further review by the independent medical monitor and sponsor:

- 1) The occurrence of at least 1 serious adverse event among any Stage 1 subject assessed by the sponsor as definitely related to the trial treatment.
- The occurrence of any severe (grade 3) solicited (local or systemic) adverse event term in > 10% of all Stage 1 subjects.

If vaccination holding rules are met at any review point, the independent medical monitor will:

- 1) Review a summary of all individual data of the relevant subject(s), including the unblinded treatment assignment, and summary safety data relative to all treatment groups; and
- 2) If there exists any imbalance that is higher in one of the two Tri-NIV treatment groups compared to the Fluzone HD group, review a detailed accounting from the investigator(s) as to the exact nature of the clinical symptoms or physical findings in the subject(s) triggering the holding rule, including any potential causation and evidence of resolution with or without treatment.

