#### Vaccination Holding Rules:

Adverse event reports meeting any one of the following 2 criteria will result in a hold being placed on subsequent enrollment and vaccinations, pending further review by the independent medical monitor and sponsor:

1) The occurrence of at least 1 serious adverse event among any Stage 1 subject assessed by the sponsor as definitely related to the trial treatment.

2) The occurrence of any severe (grade 3) solicited (local or systemic) adverse event term in > 10% of all Stage 1 subjects.

If vaccination holding rules are met at any review point, the independent medical monitor will:

1) Review a summary of all individual data of the relevant subject(s), including the unblinded treatment assignment, and summary safety data relative to all treatment groups; and

2) If there exists any imbalance that is higher in one of the two Tri-NIV treatment groups compared to the Fluzone HD group, review a detailed accounting from the investigator(s) as to the exact nature of the clinical symptoms or physical findings in the subject(s) triggering the holding rule, including any potential causation and evidence of

resolution with or without treatment.

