### 3.1.1.2 Ongoing Evaluation

In addition to the above vaccination holding rules after Stage 1, enrollment and vaccination will be suspended pending discussion with CBER and the IRB in the event of:

- Any tabulation of solicited adverse events (to be repeated approximately weekly during active enrollment) which demonstrates the occurrence of any severe (grade 3) solicited (local or systemic) adverse event term in > 10% of all subjects (note that unmonitored data will perforce be used for this tabulation), or
- 2) The occurrence of at least 1 serious adverse event in any subject assessed by the sponsor as definitely related to the trial treatment.

Nanoparticle Influenza Vaccine, Trivalent	Confidential	tNIV-E-101 Protocol
Novavax, Inc.	Version $5.0 - 13$ November 2017	Page 35

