# 8.5 Relationship (Causality)

The relationship of an AE to the test article must be assessed and documented by the investigator or a qualified sub-investigator. Based on the criteria described below, the investigator must classify the AE according to the following categories shown in Table 7.

Relationship	Relationship Description
Unrelated / Unlikely	• May or may not follow a reasonable temporal sequence from administration of the test article;
	• No plausible mechanism based on known or suspected actions of the test article or product class;
	• Readily explained by known characteristics of the subject's clinical state, common intercurrent illnesses, or other treatments administered to the subject.
Possibly	• Follows a reasonable temporal sequence from administration of the test article;
	• Based on known or suspected actions of the test article or product class, a plausible mechanism could exist;
	• May be reasonably explained by known characteristics of the subject's clinical state, common intercurrent illnesses, or other treatments administered to the subject; but the investigator deems this less likely than test article effect.
Probably	• Follows a reasonable temporal sequence from administration of the test article;
	• Based on known or suspected actions of the test article or product class, a plausible mechanism could exist;
	• Cannot be reasonably explained by known characteristics of the subject's clinical state, common intercurrent illnesses, or other treatments administered to the subject.
Definitely	• Follows a reasonable temporal sequence from administration of the test article;

 Table 7:
 Definition of Relationship for Adverse Events

Relationship	Relationship Description
	• Consistent with known actions of the test article or product class;
	• Cannot be reasonably explained by known characteristics of the subject's clinical state, common intercurrent illnesses, or other treatments administered to the subject.
	• May be confirmed by rechallenge (if applicable).

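### The only SAE trigger for a mandatory hold is a sponsor rating of *definitely related*; on the Table 7 scale, a *Probably* related SAE in this first-in-human trial would require no hold

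*Protocol*

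**What the plan says.** Protocol 3.1.1 gives the reason for the rules: "This will be a first-in-human trial with Tri-NIV formulated with Matrix-M1 adjuvant. Thus, vaccination holding rules will be used" to govern the move from Stage 1 to Stage 2. Section 3.1.1.1 lists two criteria, and meeting either one stops further enrollment and vaccinations pending review:

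- SAE limb: "at least 1 serious adverse event among any Stage 1 subject assessed by the sponsor as definitely related to the trial treatment".
- Reactogenicity limb: "The occurrence of any severe (grade 3) solicited (local or systemic) adverse event term in > 10% of all Stage 1 subjects".

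After Stage 1, section 3.1.1.2 suspends enrollment and vaccination on the same SAE threshold: "The occurrence of at least 1 serious adverse event in any subject assessed by the sponsor as definitely related to the trial treatment". The synopsis repeats both rules under Vaccination Holding Rules and Ongoing Evaluation.

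The default is stated in 3.1.1: "If vaccination holding rules are not met, the independent medical monitor will notify the sponsor Chief Medical Officer (CMO) to proceed with enrollment".

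None of these sections defines the scale on which the sponsor rates causality. The only scale in the documents is Table 7 in Protocol 8.5, which is addressed to the investigator or sub-investigator. It has four levels: Unrelated/Unlikely, Possibly, Probably and Definitely. The mechanism line for *Probably* reads "Based on known or suspected actions of the test article or product class, a plausible mechanism could exist". For *Definitely* it reads "Consistent with known actions of the test article or product class".

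**The concern.** A holding rule in a first-in-human trial is there mainly for the reaction nobody expected. Such a reaction is the hardest to rate *Definitely*, because that level asks for consistency with actions already known. The protocol itself supplies an example. Section 8.1.5 asks investigators to watch for autoimmune events because a link with immunization has been hypothesized, and says there is no current evidence either way for these products. A serious event of that kind, with suitable timing and no competing cause, could naturally be rated *Probably*.

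At stake is whether dosing of healthy adults aged 60 or over pauses automatically after such an event or continues unless the sponsor chooses to stop it. In Stage 1 the written default is to proceed. The mandatory trigger is also narrower than the trial's own notion of a related event: Protocol 10.4.1.1 counts possibly, probably and definitely as related, and SAP 12.5 counts a missing relationship as related.

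**Working it through.** The plan states no figure for the SAE rule, so there is none to reproduce. The check has three parts.

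**1. *Probably* against *Definitely* in Table 7**

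| Element | Probably | Definitely |
|---|---|---|
| Timing | reasonable sequence required | same |
| Other explanation | no reasonable one | same |
| Mechanism | known or suspected actions; plausible | consistent with known actions |
| Rechallenge | not mentioned | may confirm; not required |

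The only required difference is the mechanism line. On this scale, an SAE with good timing, no other reasonable explanation and a suspected mechanism is *Probably* and does not meet the SAE limb. An SAE consistent with known actions of the product class can be *Definitely* and does meet it.

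**2. Could the other limb catch a single SAE?**

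The Stage 1 target is 60 subjects (Protocol 3.1). 6/60 = 10.0% does not exceed 10%; 7/60 = 11.7% does. So at least 7 subjects need the same grade 3 solicited term, and one SAE cannot meet this limb. No other section of the protocol or SAP requires a hold for an SAE rated below *Definitely*.

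**3. How often would a wider trigger fire?**

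Inputs:

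- Protocol 1.9: 5,921 older adults received the same-platform RSV F antigen without adjuvant, in a trial run from 07 November 2015 to 23 November 2016. Three had SAEs that investigators called related (acute myocardial infarction, congestive cardiac failure, transient ischemic attack).
- The same section reports the sponsor's view that all the related SAEs were readily explainable by medical history or natural disease progression. In Table 7 a ready alternative explanation belongs to Unrelated/Unlikely, while *Probably* requires that no reasonable one exists.
- Tri-NIV recipients: 2 × 20 = 40 in Stage 1 and 2 × 110 = 220 overall.

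On the sponsor's view, then, none of the three would be *Probably*, and the count is 0/5,921.

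One-sided 95% upper limit: p = 1 − 0.05^(1/5,921) = 0.0506%.

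Chance of at least one event in n subjects: 1 − (1 − p)^n.

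- n = 40: 2.0%
- n = 220: 10.5%, about 11%

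If the same limit is assumed for Fluzone HD recipients, whom the rule also covers, n = 60 gives 3.0% and n = 330 gives 15.4%.

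These are upper limits, and the source fits imperfectly in both directions. The antigen was unadjuvanted, which could make the limit too low for Tri-NIV with Matrix-M1. The source trial ran for about a year, whereas the Stage 1 review covers 7 days and a suspension matters little once dosing has ended; that makes the limit too high.

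**The case against.** The strongest case against is that this is a choice of risk tolerance and not an error. No requirement in the documents is breached. The rule relies on the sponsor's rating and cites no scale, so the documents do not show that the sponsor would use Table 7 or how much *definitely* leaves out. The remaining safeguards are substantial:

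- 24-hour SAE reporting regardless of relationship (Protocol 8.3)
- an independent medical monitor who sees the Stage 1 solicited and unsolicited events (3.1.1)
- unblinding of unexpected, suspected-related SAEs (3.5), or on safety signals (SAP 1.3)
- termination at any time (Protocol 6.7) and immediate safety changes (9.5)

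The line at *Probably* is also a judgement, since in Table 7 *Possibly* already means that the rater thinks the test article the likelier cause. Finally, a hold on vaccinations could, as worded, catch the Day 21 licensed vaccine for Groups A and B.

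Much of this stands. The gap is conditional and narrow, and the sponsor can always pause voluntarily. But those safeguards are reporting or discretionary steps, and none obliges a pause. The missing scale does not rescue the rule either: if Table 7 applies, the gap exists; if it does not, the only SAE trigger rests on an undefined term. Drawing the line at *Probably* is reasonable because that level has already excluded other reasonable explanations, whereas *Possibly* admits them, and in older adults they are common. The Day 21 point is a real cost, and the fix deals with it.

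Three stronger readings are tempting, and the documents do not support them:

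- *No SAE could be rated Definitely for a product new to humans.* Table 7 also accepts known actions of the product class, and Protocol 1.7.1 and 1.9 describe human experience with the adjuvant and the platform.
- *3/5,921 is the expected rate of added holds.* It counts investigator ratings, not split by level, for events the sponsor considered explainable. One placebo subject also had SAEs rated related.
- *The zero related SAEs among 896 Matrix-M1 recipients imply a large chance.* The limit 1 − 0.05^(1/896) = 0.334% gives 12.5% for 40 and 52% for 220. These figures reflect the size of the sample and not any observed event, cover all levels of relatedness, and draw on some trials that are ongoing and may be blinded. They are not expectations.

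**Conclusion.** The concern holds in a limited form. The only SAE trigger for a mandatory hold or suspension is a sponsor rating of *definitely related* on an unstated scale. If Table 7 is that scale, a *Probably* related SAE requires no hold. The gap is confined to serious reactions not shown to be consistent with known actions of the product or its class.

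Such an event is unlikely. The documents give no rate for it. The best available bound is at most about 2% among 40 and 11% among 220 Tri-NIV recipients, assuming that the sponsor's reading of the three RSV F events is accepted and that the unadjuvanted, year-long experience carries over. The same bound measures both the benefit (a hold that would otherwise not be required) and the cost (an added pause).

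A reader might infer that dosing would continue unchecked after such an event. The documents do not say so: the sponsor would have the report within 24 hours and could stop. What is missing is the obligation to stop. This is a cheap improvement of low-to-moderate priority.

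**What to change.** In Protocol 3.1.1.1 and 3.1.1.2, and in the synopsis under Vaccination Holding Rules and Ongoing Evaluation, replace *definitely related* with *probably or definitely related (Table 7)*. Leave the rating with the sponsor, and keep the Stage 1 and any-subject scopes as they are. Citing Table 7 also settles which scale the sponsor uses.

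Add one sentence saying that a hold does not by itself delay the Day 21 licensed rescue vaccine. To protect the blind, the same should apply to the matching saline injection in Group C.

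The cost is a protocol amendment with IRB approval and a small added chance of a temporary pause, within the bounds above. Under 3.1.1, a Stage 1 pause brings unblinding, a report and recommendation, and IRB approval before enrollment resumes. Under 3.1.1.2, a suspension brings discussion with CBER and the IRB. Keeping the rating with the sponsor limits pauses for events explained by a subject's medical history.

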# 3.4 Maintaining the Blinded Randomization Scheme

Randomization procedures will be performed by IWRS, with treatment assignments known only to the responsible unblinded vaccine administrators at the trial center. Subjects and the main trial team clinical staff will remain blinded for the duration of the trial unless emergency unblinding is necessary. Refer to Section 3.5 for information regarding the process for emergency unblinding.

All treatment assignments, vaccine storage and accountability, and/or dosing-related matters will be monitored by a designated "unblinded monitor". Any deviations will be discussed, documented, and resolved by the unblinded monitor and the unblinded site personnel. Reports provided by the unblinded monitor will be reviewed by designated unblinded personnel at either

Novavax or the clinical research organization (CRO), not involved with the main trial team. No reports from the unblinded monitor will be released to the Trial Master File (TMF) until database lock for Day 364 and official declaration of unblinding is given by Novavax.

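### The investigator's case account after a hold is prescribed only for an undefined imbalance against Tri-NIV, seen after unblinding; asking for it then could signal that direction to blinded sites

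*Protocol*

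**What the plan says.** Protocol 3.1.1.1 sets two triggers in Stage 1, which has about 60 subjects, about 20 per group:

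- a serious adverse event that the sponsor attributes definitely to treatment (one is enough);
- "The occurrence of any severe (grade 3) solicited (local or systemic) adverse event term in > 10% of all Stage 1 subjects".

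Once either is met, the independent medical monitor has two steps.

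- Step 1 has no condition: "Review a summary of all individual data of the relevant subject(s), including the unblinded treatment assignment", plus summary safety data for all groups.
- Step 2 opens with a condition: "If there exists any imbalance that is higher in one of the two Tri-NIV treatment groups compared to the Fluzone HD group". Only then does it call for the investigators' detailed accounting "as to the exact nature of the clinical symptoms or physical findings in the subject(s) triggering the holding rule". That accounting is also to address possible causes and whether the events resolved.

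The synopsis repeats both steps. Section 3.1.1 requires the monitor and the sponsor to review the unblinded data after any hold and to recommend resuming, amending or terminating, whichever way the groups differ.

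On blinding, section 3.4 says: "Subjects and the main trial team clinical staff will remain blinded for the duration of the trial unless emergency unblinding is necessary". Section 10.6.1 keeps site personnel blinded until Day 364. Section 3.5 lets the sponsor's Chief Medical Officer or an investigator ask to unblind subjects who contributed to a holding rule.

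**The concern.** There are two linked problems.

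**Case information depends on group results.** A recommendation is due after every hold, but the investigators' narrative is prescribed for one direction of imbalance only. If Fluzone HD has as many cases as each Tri-NIV group, or more, no account is prescribed for any triggering subject, including those who received Tri-NIV. For the grade 3 trigger, section 8.1.1 does not ask investigators to judge causality of solicited events in the diary window. Step 2 is therefore where a causation view would come from.

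**The request can carry a signal.** Investigators hold the protocol. If they know that the account is called for only when Tri-NIV is higher, being asked, or not being asked, tells them something about the allocation. They go on to judge severity and causality of unsolicited events, and of medically attended events, significant new medical conditions and serious events, for up to a year. These are primary safety data.

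**Working it through.** The plan gives no figure for this step, so there is none to reproduce beyond its own threshold.

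**Inputs from the plan.** Stage 1: 60 subjects, 20 per group (3.1 and Table 1). Grade 3 trigger: more than 10% of all Stage 1 subjects. Since 6/60 is exactly 10%, the smallest triggering count is 7.

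**Assumptions.** The imbalance is read as a count: triggering cases in A exceed those in C, or those in B exceed those in C. Groups are exactly 20 each. Risk is equal in all groups unless stated. The account is requested after the check, and the investigator knows the rule.

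**Formula.** With m triggering subjects split as a, b, c over groups A, B, C, P(a, b, c) = C(20,a)·C(20,b)·C(20,c) / C(60,m). Add over all splits with a > c or b > c to get the probability that an account is prescribed.

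**One serious adverse event (m = 1).** Before any request, P(Tri-NIV) = 40/60 = 0.67. The condition is met exactly when the subject is in A or B. A request therefore gives P(Tri-NIV) = 1.00, and no request means Fluzone HD. The dose is not revealed.

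**Seven grade 3 cases (m = 7).** C(60,7) = 386,206,920. The splits that do not meet the condition are those with a ≤ c and b ≤ c. Their weights sum to 154,727,640, so P(no account) = 154,727,640 / 386,206,920 = 0.401 and P(account) = 0.599.

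- Expected Tri-NIV share of cases: 0.778 with an account, 0.500 without.
- Check: 0.599 × 0.778 + 0.401 × 0.500 = 0.667, the prior share.
- Largest number of Tri-NIV cases with no account: 4 of 7 (for example 2, 2, 3).
- Given an account, at least one Fluzone HD case is among those described with probability 0.92.

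| Triggering cases | P(account prescribed) | P(no account) | P(case is Tri-NIV, given account) |
|---|---|---|---|
| 7 | 0.599 | 0.401 | 0.778 |
| 8 | 0.561 | 0.439 | 0.774 |
| 10 | 0.604 | 0.396 | 0.754 |
| 12 | 0.579 | 0.421 | 0.746 |

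**If Tri-NIV risk is truly higher.** Multiply each weight by OR^(a+b) and renormalise, with m = 7. P(no account) falls from 40% to about 14% at an odds ratio of 2, 6.5% at 3 and 2% at 5. These odds ratios are illustrative.

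**How often a hold would occur.** For one solicited term with the same true grade 3 rate in all 60 subjects, P(7 or more) is 1.0% at a rate of 4%, 3.0% at 5% and 39% at 10%. These rates are assumed too. Many terms are solicited, so the chance that some term triggers is higher than for one term.

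**The case against.** The case for leaving the text alone has real weight. Tri-NIV is the first-in-human product and Fluzone HD is licensed, so looking harder when Tri-NIV is worse is a reasonable priority. The 40% figure assumes equal risk, where there is no Tri-NIV excess to miss. Step 2 sets a minimum, and nothing stops the monitor from asking for more.

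A reader might infer two stronger claims, and the documents support neither.

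- *That case detail depends on the arm a subject was in.* The condition is on groups, not subjects. Once it is met, the account covers all triggering subjects, Fluzone HD recipients included. Much is also collected in every group regardless: the step 1 summary of individual data, the Day 3 query and Stage 1 Day 7 visit (6.1.3, 6.1.4), follow-up of continuing solicited events to resolution (8.1.1), and supporting detail and causality for all serious events (8.3, 8.5). What can be missing is a supplementary narrative, mainly on nature and potential causation of grade 3 solicited events.
- *That the request itself discloses allocation.* Section 3.1.1.1 says the monitor reviews an accounting. It does not say when or by whom it is requested. If sites supplied it as soon as the hold was placed, nothing would leak. Even when requested after the check, it identifies a subject as Tri-NIV only where every triggering case must be Tri-NIV, as with a single serious event, and the investigator would need to know that no other case triggered the hold. Otherwise it shifts a probability. Section 3.5 also already allows these subjects to be unblinded on request.

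What remains is that section 3.5 describes a documented unblinding request, with a stated rationale for individual subjects. It does not cover an unintended signal to sites that are meant to stay blinded, and nothing in the documents masks the reason for asking.

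**Conclusion.** The point holds in limited form. An undefined, one-directional imbalance, visible only after unblinding, decides whether the investigators' account is prescribed, although a recommendation is due after every hold. If sites are asked after that check, the request can reveal the direction of the imbalance: with certainty as to Tri-NIV receipt after a single triggering serious event, and only from 67% to 78% for seven grade 3 cases.

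The figures rest on equal risk, exact groups of 20, a count-based reading of the imbalance, and a request made after the check. If the imbalance were read as any difference in any safety summary, the condition would be met more often, and both the gap and the signal would be smaller. That the reading is open is itself part of the problem. The issue is contingent on a hold and is of low priority.

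**What to change.** In 3.1.1.1 and the synopsis, delete the imbalance condition. State instead that, when a holding rule is met, the detailed accounting (nature, potential causation, evidence of resolution) is requested at once, by staff blinded to assignment, for every triggering subject whatever the group. State also that this runs in parallel with the unblinded review and does not delay it. Asking for every case at the moment of the hold removes both the dependence on group results and the signal to sites.

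Reconcile the new wording with 3.1.1 (pause and unblinding request), 3.4 (site blinding) and 3.5 (unblinding of contributing subjects). The holding thresholds do not change.

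The cost is a short protocol amendment and, if a hold occurs, a few extra case accounts: about 7 at the smallest grade 3 trigger.
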